5.1.2 Subject Inclusion Criteria

In order to be eligible for participation in this trial, the subject must:

1. Biopsy-proven, previously untreated stage III or IV squamous cell carcinoma of the larynx, Primary tumor stage (T2, T3) and nodal stage (N0,N1,N2,N3).
2. Be willing and able to provide written informed consent/assent for the trial.
3. Be ≥ 18 years of age on day of signing informed consent.
4. Have measurable disease based on RECIST 1.1.
5. Be willing to provide tissue from a newly obtained core or excisional biopsy of a tumor lesion. *Newly-obtained is defined as a specimen obtained up to 6 weeks (42 days) prior to initiation of treatment on Day 1. Subjects for whom newly-obtained samples cannot be provided (e.g. inaccessible or subject safety concern) may submit an archived specimen only upon agreement from the Sponsor.*
6. Have a performance status of 0 or 1 on the ECOG Performance Scale.
7. Anticipated survival minimum 12 months.
8. Patient is > 5 years free of another primary malignancy, except: a) if the other malignancy is basal cell carcinoma or cervical carcinoma in situ or b) if the other primary malignancy is not considered clinically significant and is requiring any active intervention
9. Demonstrate adequate organ function as defined in Table 1, all screening labs should be performed within 10 days of treatment initiation.

Table 1 Adequate Organ Function Laboratory Values

System	Laboratory Value
Hematological	
Absolute neutrophil count (ANC)	$\geq 1,500$ /mcL
Platelets	$\geq 100,000$ / mcL
Hemoglobin	≥ 9 g/dL or ≥ 5.6 mmol/L without transfusion or EPO dependency (within 7 days of assessment)
Renal	
Serum creatinine OR Measured or calculated ^a creatinine clearance (GFR can also be used in place of creatinine or CrCl)	≤ 1.5 X upper limit of normal (ULN) OR ≥ 60 mL/min for subject with creatinine levels > 1.5 X institutional ULN
Hepatic	
Serum total bilirubin	≤ 1.5 X ULN OR

	Direct bilirubin \leq ULN for subjects with total bilirubin levels $>$ 1.5 ULN
AST (SGOT) and ALT (SGPT)	\leq 2.5 X ULN OR \leq 5 X ULN for subjects with liver metastases
Albumin	\geq 2.5 mg/dL
Coagulation	
International Normalized Ratio (INR) or Prothrombin Time (PT)	\leq 1.5 X ULN unless subject is receiving anticoagulant therapy as long as PT or PTT is within therapeutic range of intended use of anticoagulants

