5.2.1.3 Dose Modification for Cisplatin

1. Neutropenia: If on the day of scheduled treatment with cisplatin the absolute neutrophil count (ANC) is $< 1200/\text{mm}^3$, hold the second chemotherapy treatment but not the radiation until $\text{ANC} \geq 1200/\text{mm}^3$, then treat at 100% dose. Neutropenic fever (i.e. any fever $> 38.5^\circ\text{C}$ with an $\text{ANC} < 1000/\text{mm}^3$) will require a 25% dose reduction of the next cisplatin dose. If neutropenic fever occurs with both the first and second dose, cisplatin should be discontinued.
2. Thrombocytopenia: If on the day of scheduled treatment with cisplatin the platelet count is $< 75,000/\text{mm}^3$, hold chemotherapy treatment but not the radiation until platelets are $\geq 75,000/\text{mm}^3$, then treat at 100% dose. Thrombocytopenia that results in bleeding will require a 25% dose reduction of the following cisplatin dose.
3. Neurotoxicity: If grade 2 neurotoxicity develops, hold cisplatin (but continue RT) until toxicity improves to \leq grade 1, then reduce the following cisplatin dose to 80 mg/m^2 . If any signs of grade 3 or greater neurotoxicity occur, discontinue cisplatin, but continue RT.
4. Renal Adverse Events: Cisplatin dose should be based on creatinine clearance immediately prior to the second and third cisplatin dose using the following guidelines:
Note: Creatinine clearance must be calculated (Cockcroft-Gault) in order to make dose adjustment. If the calculated clearance is 50 mL/min or above, a 24-hour urine collection is not needed, but if the calculation is less than 50 mL/min , a 24-hour urine collection is mandated, and the cisplatin dose will be determined as follows:
Creatinine Clearance Cisplatin Dose
 $> 50 \text{ ml}/\text{min}$ then administer 100 mg/m^2
40-50 ml/min then administer 50 mg/m^2
 $< 40 \text{ ml}/\text{min}$ Hold drug*
*Cisplatin should be held (but the RT continued) and the creatinine measured weekly, until creatinine clearance is $> 50 \text{ ml}/\text{min}$, and then the next and following doses of cisplatin should be given at the reduced dose of 50 mg/m^2 .
5. Nausea and Vomiting: Maximum supportive therapy will be given, and cisplatin will be continued at full dose for \leq grade 2 nausea and vomiting. For grade 3 nausea and vomiting refractory to supportive therapy, cisplatin will be held until recovery to $<$ grade 2. No dose reductions will be made.

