6. Mucositis: Significant mucositis (grade 3-4, CTCAE, v. 4) is expected from radiation and cisplatin and should not be a reason for a treatment break, unless it significantly interferes with fluid intake or nutrition. Aggressive supportive care is encouraged as well as consideration of a PEG tube if not already done.
7. Ototoxicity: For clinical hearing loss not requiring a hearing aid, reduce cisplatin to 50 mg/m^2 . For hearing loss requiring a hearing aid, discontinue cisplatin. For grade 2-3 tinnitus (CTCAE, v. 4) at the time of retreatment, hold cisplatin until improvement to grade 1 or less and then reduce the following doses of cisplatin to 50 mg/m^2 . If tinnitus does not improve to grade 1 or less by the last day of

radiation therapy, discontinue cisplatin. An audiogram is recommended when there is any report of significant change in hearing and/or an increase in tinnitus.

8. Other Toxicities: For any other grade 3-4 adverse events, hold cisplatin until toxicities have recovered to grade 1 or less.

If the second or third dose of cisplatin is delayed more than 21 days because of hematologic, neurologic, renal, or other adverse events, that dose will be omitted. If a weight change of $\geq 10\%$ occurs, the following cisplatin doses should be adjusted.

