5.2.1.4 Timing of Dose Administration

Trial treatment should be administered on Day 1 of each cycle after all procedures/assessments have been completed as detailed on the Trial Flow Chart (Section 6.0). Trial treatment may be administered up to 2 days before or after the scheduled Day 1 of each cycle due to administrative reasons. Day 1 cisplatin and radiation can begin up to 7 days earlier (minimum 14 days after pembrolizumab administration) if patient and /or investigator prefer to expedite initiation of radiation.

All trial treatments will be administered on an outpatient basis.

Initiation of subsequent cycles of pembrolizumab therapy may be delayed for up to 6 weeks to allow recovery from all drug-related toxicity. If the subsequent dose of pembrolizumab is delayed more than 6 weeks because of adverse events, pembrolizumab will be discontinued. Initiation of subsequent cycles of cisplatin therapy may be delayed for up to 3 weeks to allow recovery from all drug-related toxicity. If the subsequent dose of cisplatin is delayed more than 21 days because of adverse events, that dose will be omitted. Alternately, the Investigator may choose to administer supportive care (blood product transfusions) for retreatment criteria to be met. If the recovery criteria are not met after a 6-week delay, the patient will be discontinued from study treatment unless, in the opinion of the Investigator, the patient is experiencing a clinical benefit, in which case a decision regarding continuation of treatment will be made on an individual patient basis in consultation with the Merck medical monitor. Justification will be recorded in the source documents.

In the setting of dose delays, neither cisplatin nor pembrolizumab will be administered following completion of radiation therapy.

When initiating a subsequent cycle, a minimum interval of 21 days should be observed between pembrolizumab administrations and between cisplatin administrations.

Cisplatin or pembrolizumab can be given either before or after the radiation therapy fraction that is given on the same day. If radiation is held for more than 2 days (for any reason), cisplatin may be held as well until radiation resumes.

Note: pembrolizumab or cisplatin given within 48 hours of days 1 and 22 and 43 due to holidays, for example, is acceptable). Weekends count as days. Use the actual body weight for all patients. There should be no dose modifications because of obesity.

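### The plan sets no creatinine-clearance threshold for the first cisplatin dose, so 100 mg/m² is not prevented at a clearance where its own rule would halve or hold a later dose

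*Combined protocol and SAP*

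**What the plan says.** **Entry.** The renal row of Table 1 (section 5.1.2) reads "≤ 1.5 X upper limit of normal (ULN) OR ≥ 60 mL/min for subject with creatinine levels > 1.5 X institutional ULN". The clearance limb applies only to patients whose creatinine is above 1.5 x ULN. GFR may replace creatinine or clearance, but need not. Footnote a leaves the clearance calculation to institutional standard.

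**Dosing.** Section 5.2.1.3 item 4 states: "Cisplatin dose should be based on creatinine clearance immediately prior to the second and third cisplatin dose using the following guidelines". If the Cockcroft-Gault value is below 50 mL/min, "a 24-hour urine collection is mandated, and the cisplatin dose will be determined as follows": 100 mg/m² above 50, 50 mg/m² at 40-50, hold below 40. On the hold: "Cisplatin should be held (but the RT continued) and the creatinine measured weekly, until creatinine clearance is" above 50 mL/min, after which doses resume at 50 mg/m².

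**Omission.** "If the second or third dose of cisplatin is delayed more than 21 days because of hematologic, neurologic, renal, or other adverse events", that dose is dropped. Section 5.2.1.4 repeats this for a subsequent dose and adds that "neither cisplatin nor pembrolizumab will be administered following completion of radiation therapy".

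**First dose.** Section 2.1 and Table 2 plan 100 mg/m². Section 5.2.1.4 gives treatment "after all procedures/assessments have been completed as detailed on the Trial Flow Chart", and the chart schedules a chemistry panel at C1 D1. No section states a clearance at which the first dose is reduced or held.

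**The concern.** Item 4 works on absolute clearance, not on change from baseline. It therefore does more than manage kidney injury that appears on treatment: it states a level of function at which the plan regards 100 mg/m² as too much. That level is not applied to the one dose given before any cisplatin exposure, and entry on the creatinine route does not enforce it either.

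A first dose cannot be taken back. At a confirmed 40-50 mL/min it would be twice what item 4 gives at the next cycle; below 40 it would be a dose that item 4 holds. A patient whose clearance stays below 40 would then have doses 2 and 3 held and finally dropped.

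Timing adds to this. Section 5.1.2 requires screening labs within 10 days of treatment initiation, which is the first pembrolizumab dose, and cisplatin normally follows 14 to 21 days later. The creatinine that established eligibility can thus be up to 10 + 21 = 31 days old at the first cisplatin dose.

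**Working it through.** The plan states no figure to reproduce. The check has two parts: what the rules do to one patient with unchanging renal function, and whether the creatinine route can admit such a patient.

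**1. Same confirmed clearance at every cycle (mg/m²)**

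| Clearance | Dose 1 | Dose 2 | Dose 3 | Total, if dose 1 is given as planned |
|---|---|---|---|---|
| above 50 | 100 | 100 | 100 | 300 |
| 45 | 100, no rule | 50 | 50 | 100 + 50 + 50 = 200 |
| 38 | 100, no rule | hold, then omit | hold, then omit | 100 |

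**2. Can creatinine ≤1.5 x ULN coexist with clearance below 50?**

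The plan names Cockcroft-Gault: (140 − age) x weight / (72 x creatinine), times 0.85 for women. ULN, age and weight are not in the documents and are assumed here; creatinine is in mg/dL.

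*Man, 65 years, 70 kg:* 75 x 70 / 72 = 72.9.
- At the eligibility limit for ULN 1.0 / 1.1 / 1.2 / 1.3: 72.9 divided by 1.50 / 1.65 / 1.80 / 1.95 = 48.6 / 44.2 / 40.5 / 37.4 mL/min.
- Item 4 would require a urine collection above creatinine 72.9/50 = 1.46. The hold tier starts above 72.9/40 = 1.82.
- He can be eligible in the hold tier only if ULN exceeds 1.823/1.5 = 1.215.
- The eligible band below 50 mL/min is 1.46-1.50 at ULN 1.0 and 1.46-1.80 at ULN 1.2.
- At a calculated 40.5, a measured clearance more than 50/40.5 − 1 = 23% higher would restore full dose.

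*Woman, 65 years, 60 kg:* 75 x 60 x 0.85 / 72 = 53.1.
- At the limit for ULN 0.9 / 1.0 / 1.1: 39.4 / 35.4 / 32.2 mL/min.
- Urine collection above creatinine 1.06; hold tier above 1.33.

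*Men at creatinine 1.8 (the limit if ULN is 1.2), mL/min:*

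| Age | 60 kg | 70 kg | 80 kg | 90 kg |
|---|---|---|---|---|
| 55 | 39.4 | 45.9 | 52.5 | 59.0 |
| 65 | 34.7 | 40.5 | 46.3 | 52.1 |
| 75 | 30.1 | 35.1 | 40.1 | 45.1 |

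Nine of 12 are below 50. The count depends on placing every man at the limit: over the same ages and weights it is 6 of 12 at creatinine 1.5 (the limit if ULN is 1.0), and 1 of 12 at creatinine 1.2 (75 years, 60 kg: 45.1).

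**3. Ordering of the two entry routes.** With ULN 1.2, a man of 55 weighing 90 kg at creatinine 1.81 has 85 x 90 / (72 x 1.81) = 58.7 mL/min and fails the 60 mL/min limb. A man of 75 weighing 60 kg at 1.80 has 65 x 60 / (72 x 1.80) = 30.1 mL/min and is admitted.

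**The case against.** Item 4 is headed as a renal adverse-event rule and sits in a dose-modification section. On that view the first dose belongs to eligibility, pre-dose review and standard practice, and whether later-dose cut-offs should apply at baseline is a clinical choice. The safeguards are real: section 7.1.3 requires lab results to be reviewed and judged acceptable before each dose; section 5.1.1 requires candidacy for curative chemoradiation; exclusion 15 lets the investigator turn a patient away; section 2.1 ties cisplatin to standard of care; section 5.6.2 requires hydration; and section 9.6 refers to the cisplatin package insert.

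Much of this stands. A reader might infer that the plan compels a full first dose in a patient with poor clearance. It does not; it fails to prevent one. The insert is not among the documents, so the absence of a threshold can be asserted only for the visible text. What does not stand is that judgement makes a number unnecessary: the same judgement is available before doses 2 and 3, and there the plan adds thresholds and a mandatory urine collection.

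A reader might also infer that the data for a first-dose rule are already in hand. The documents do not establish that. Table 5, as it reads here, lists blood urea nitrogen but no creatinine (possibly lost when the text was extracted), and section 7.1.5.2 lets day-1 assessments be done up to 3 weeks earlier without saying which day 1 it means.

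**Conclusion.** The gap is real and should be fixed. On the visible text, 100 mg/m² at dose 1 is not prevented at a confirmed clearance where item 4 gives 50 mg/m² (40-50 mL/min) or nothing (below 40) at a later dose. Confidence in that reading is high.

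Its frequency is unknown. The worked cases sit mostly at the creatinine limit, use assumed ULNs, and give calculated clearances that a 24-hour urine could overturn. They show that the gap can be reached at ordinary ages and weights, not that many patients will fall in it; the 9 of 12 is not a prevalence. A reader might infer an effect on laryngectomy-free survival, but nothing in the documents supports estimating one. The point concerns first-dose safety and consistency of dosing.

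**What to change.** 1. **Item 4 of 5.2.1.3.** Extend the clearance rule to the first cisplatin dose, with the same urine confirmation below 50 mL/min. Name serum creatinine explicitly in the C1 D1 panel and require it to be current. Section 5.2.1.4 says "Trial treatment may be administered up to 2 days before or after the scheduled Day 1 of each cycle", which gives some room for the collection. Because section 5.2.2.1 starts radiotherapy on Monday to Wednesday, drawing the creatinine shortly before C1 D1 is safer than relying on that window.

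2. **Omission rule.** Extend the more-than-21-day rule in 5.2.1.3 and 5.2.1.4 to a held first dose. It now covers only the second, third or a subsequent dose, so adding one word to item 4 would leave a held first dose without an end point.

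3. **Table 1.** At screening, before the first pembrolizumab dose, require Cockcroft-Gault clearance above 50 mL/min, urine-confirmed if below 50, for patients entering on creatinine ≤1.5 x ULN. Keep the 60 mL/min limb for creatinine above 1.5 x ULN; replacing it with 50 would loosen entry. State that Cockcroft-Gault overrides footnote a for this check. Without this step, a patient stable at 38 mL/min would start pembrolizumab and then, under step 1, receive no cisplatin.

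Cost: a small text amendment, one calculation per patient, and an occasional urine collection, reduced or held first dose, or screen failure.

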5.1.3 Subject Exclusion Criteria

The subject must be excluded from participating in the trial if the subject:

1. Patients with T1 primary tumor or T4 large volume tumor that has resulted in larynx dysfunction at baseline (for example tumor largely penetrating into base of tongue and resulting in inability to swallow at baseline)
2. Prior radiation therapy to larynx area or involved neck.
3. Distant metastasis. Small lesions (for example, small nodule in lung) that are not clinically or radiographically suggestive of metastasis do not require biopsy for confirmation.
4. Prior complications from former therapies, such as history of radiation pneumonitis that, in the opinion of the investigator, may have risk of increasing toxicity with anti-PD1 therapy.
5. Is currently participating and receiving study therapy or has participated in a study of an investigational agent and received study therapy or used an investigational device within 4 weeks of the first dose of treatment.

6. Has a diagnosis of immunodeficiency or is receiving systemic steroid therapy or any other form of immunosuppressive therapy within 7 days prior to the first dose of trial treatment.
7. Has a known history of active TB (Bacillus Tuberculosis)
8. Hypersensitivity to pembrolizumab or any of its excipients.
9. Patients who have not recovered (i.e., \leq Grade 1 or at baseline) from adverse events due to a previously administered agent.
 - Note: Subjects with \leq Grade 2 neuropathy are an exception to this criterion and may qualify for the study.
 - Note: If subject received major surgery, they must have recovered adequately from the toxicity and/or complications from the intervention prior to starting therapy.
10. Has a known additional malignancy that is progressing or requires active treatment. Exceptions include basal cell carcinoma of the skin or squamous cell carcinoma of the skin that has undergone potentially curative therapy or in situ cervical cancer.
11. Has known active central nervous system (CNS) metastases and/or carcinomatous meningitis. Subjects with previously treated brain metastases may participate provided they are stable (without evidence of progression by imaging for at least four weeks prior to the first dose of trial treatment and any neurologic symptoms have returned to baseline), have no evidence of new or enlarging brain metastases, and are not using steroids for at least 7 days prior to trial treatment. This exception does not include carcinomatous meningitis which is excluded regardless of clinical stability.
12. Has active autoimmune disease that has required systemic treatment in the past 2 years (i.e. with use of disease modifying agents, corticosteroids or immunosuppressive drugs). Replacement therapy (eg., thyroxine, insulin, or physiologic corticosteroid replacement therapy for adrenal or pituitary insufficiency, etc.) is not considered a form of systemic treatment.
13. Has known history of, or any evidence of active, non-infectious pneumonitis.
14. Has an active infection requiring systemic therapy.
15. Has a history or current evidence of any condition, therapy, or laboratory abnormality that might confound the results of the trial, interfere with the subject's participation for the full duration of the trial, or is not in the best interest of the subject to participate, in the opinion of the treating investigator.
16. Has known psychiatric or substance abuse disorders that would interfere with cooperation with the requirements of the trial.
17. Is pregnant or breastfeeding, or expecting to conceive or father children within the projected duration of the trial, starting with the pre-screening or screening visit through 120 days after the last dose of trial treatment.
18. Has received prior therapy with an anti-PD-1, anti-PD-L1, or anti-PD-L2 agent.
19. Has a known history of Human Immunodeficiency Virus (HIV) (HIV 1/2 antibodies).
20. Has known active Hepatitis B (e.g., HBsAg reactive) or Hepatitis C (e.g., HCV RNA [qualitative] is detected).
21. Has received a live vaccine within 30 days of planned start of study therapy.

Note: Seasonal influenza vaccines for injection are generally inactivated flu vaccines and are allowed; however intranasal influenza vaccines (e.g., Flu-Mist®) are live attenuated vaccines, and are not allowed.

5.2 Trial Treatments

The treatment to be used in this trial is outlined below in Table 2

Table 2 Trial Treatments

Drug	Dose/Potency	Dose Frequency	Route of Administration	Regimen/Treatment Period	Use
pembrolizumab	200 mg	Q3W	IV infusion	Starting 3W (-1 w) prior to chemotherapy, then Day 1 of each 3 week cycle Maximum 4 doses	Experimental
cisplatin	100 mg /m ²	Q3W	IV infusion	Day 1 of each 3 week cycle Maximum 3 dose	Standard
radiation	70 Gy/35fx	5 days /W	radiation	7 weeks	Standard

Trial treatment should begin on the day of randomization or as close as possible to the date on which treatment is allocated/assigned.

5.2.1 Dose Selection/Modification

5.2.1.1 Dose Selection

The rationale for selection of doses to be used in this trial is provided in Section 4.0 – Background and Rationale.

Pembrolizumab will be dosed as a flat dose.

Details on preparation and administration of pembrolizumab (MK-3475) are provided in the Pharmacy Manual.

5.2.1.2 Dose Modification for Pembrolizumab

Adverse events (both non-serious and serious) associated with pembrolizumab exposure may represent an immunologic etiology. These adverse events may occur shortly after the first dose or several months after the last dose of treatment. Pembrolizumab must be withheld for drug-related toxicities and severe or life-threatening AEs as per Table 3 below. See Section 5.6.1 and Events of Clinical Interest Guidance Document for supportive care guidelines, including use of corticosteroids.

Table 3
Dose Modification Guidelines for Pembrolizumab-Related Adverse Events

Toxicity	Hold Treatment For Grade	Timing for Restarting Treatment	Discontinue Subject
Diarrhea/Colitis	2-3	Toxicity resolves to Grade 0-1.	Toxicity does not resolve within 6 weeks of last dose or inability to reduce corticosteroid to 10 mg or less of prednisone or equivalent per day within 6 weeks.
	4	Permanently discontinue	Permanently discontinue
AST, ALT, or Increased Bilirubin	2	Toxicity resolves to Grade 0-1	Toxicity does not resolve within 6 weeks of last dose.
	3-4	Permanently discontinue (see exception below) ¹	Permanently discontinue
Type 1 diabetes mellitus (if new onset) or Hyperglycemia	T1DM or 3-4	Hold pembrolizumab for new onset Type 1 diabetes mellitus or Grade 3-4 hyperglycemia associated with evidence of beta cell failure.	Resume pembrolizumab when patients are clinically and metabolically stable.
Hypophysitis	2-3	Toxicity resolves to Grade 0-1	Toxicity does not resolve within 6 weeks of last dose or inability to reduce corticosteroid to 10 mg or less of prednisone or equivalent per day within 6 weeks.
	4	Permanently discontinue	Permanently discontinue
Hyperthyroidism	3	Toxicity resolves to Grade 0-1	Toxicity does not resolve within 6 weeks of last dose or inability to reduce corticosteroid to 10 mg or less of prednisone or equivalent per day within 6 weeks.
	4	Permanently discontinue	Permanently discontinue
Hypothyroidism	2-4	Therapy with pembrolizumab can be continued while treatment for the thyroid disorder is instituted	Therapy with pembrolizumab can be continued while treatment for the thyroid disorder is instituted.

Toxicity	Hold Treatment For Grade	Timing for Restarting Treatment	Discontinue Subject
Infusion Reaction	3-4	Permanently discontinue	Permanently discontinue
Pneumonitis	2	Toxicity resolves to Grade 0-1	Toxicity does not resolve within 6 weeks of last dose or inability to reduce corticosteroid to 10 mg or less of prednisone or equivalent per day within 6 weeks.
	3-4	Permanently discontinue	Permanently discontinue
Renal Failure or Nephritis	2	Toxicity resolves to Grade 0-1	Toxicity does not resolve within 6 weeks of last dose or inability to reduce corticosteroid to 10 mg or less of prednisone or equivalent per day within 6 weeks.
	3-4	Permanently discontinue	Permanently discontinue
All Other Drug-Related Toxicity ²	3 or Severe	Toxicity resolves to Grade 0-1	Toxicity does not resolve within 6 weeks of last dose or inability to reduce corticosteroid to 10 mg or less of prednisone or equivalent per day within 6 weeks.
	4	Permanently discontinue	Permanently discontinue

Note: Permanently discontinue for any severe or Grade 3 drug-related AE that recurs or any life-threatening event.

¹ For patients with liver metastasis who begin treatment with Grade 2 AST or ALT, if AST or ALT increases by greater than or equal to 50% relative to baseline and lasts for at least 1 week then patients should be discontinued.

² Patients with intolerable or persistent Grade 2 drug-related AE may hold study medication at physician discretion. Permanently discontinue study drug for persistent Grade 2 adverse reactions for which treatment with study drug has been held, that do not recover to Grade 0-1 within 6 weeks of the last dose.

Dosing interruptions are permitted in the case of medical / surgical events or logistical reasons not related to study therapy (e.g., elective surgery, unrelated medical events, patient vacation, and/or holidays). Subjects should be placed back on study therapy within 3 weeks of the scheduled interruption, unless otherwise discussed with the Sponsor. The reason for interruption should be documented in the patient's study record.

